## 2.2 Purpose of the Study

The purpose of this clinical study is to compare the profile of nicotine uptake (rate and extent of nicotine absorbed) after single use of THS 2.2 and CC in smoking, healthy subjects. THS 2.2 will also be compared with the nicotine nasal spray (NNS) product, used as a reference point.

## 2.3 Anticipated Benefits and Risks

### 2.3.1 Anticipated Benefits

Research conducted by the United Kingdom National Health Service has shown that up to 75% of smokers want to quit. Despite associated health risks, however, only 2% of smokers make a cessation attempt each year. Advice on health risks associated with smoking and smoking cessation advice will be provided at Screening, at Admission, and at the Day of Discharge. The advice will follow the recommendations by the World Health Organization ([Raw et al, 2002](#)). Subjects who are motivated to quit smoking during the study will be given the opportunity to continue their smoking cessation attempt and will be referred to appropriate smoking cessation services for continuing support and counselling at a higher level. Subjects who participate in this study will also benefit from repeated, detailed health check-ups, which may help to uncover undiagnosed medical conditions.

### 2.3.2 Anticipated Foreseeable Risks due to Study Procedures

- Risks related to blood sampling, e.g., excessive bleeding, fainting, haematoma, paresthesia, or infection.
- Risks related to chest X-rays, e.g., a small increase of risk to develop cancer later in life.
- Risks related to drug application as part of testing procedures (i.e., spirometry with short-acting bronchodilator at Screening) per study protocol and scientifically accepted standards.

### **2.3.3 Anticipated Foreseeable Risks due to Investigational Product (THS 2.2 and CC) or Reference Point Product (NNS)**

- Change in smoking habits due to study requirements and related concomitant symptoms, e.g., craving.
- Risks specific to the use of any NNS, as per the relevant summary of product characteristics.

All risks related to study procedures, investigational product (IP), reference product or support for smoking abstinence will be explained in detail to the subjects. Mitigation will include, but will not be limited to:

- Close monitoring and medical evaluation of potential safety signals throughout the study and follow-up.
- Using accepted research and scientific standards e.g., blood samples not to exceed blood donation standards.
- Management and follow-up of adverse events (AEs)/serious adverse events (SAEs).

### **2.3.4 Unforeseeable Risks**

As with any IP, reference product or support for smoking abstinence, there may be unforeseeable risks and hazards that could occur. The possibility of such will be explained at Screening, Admission, and Day of Discharge. Mitigation will include close monitoring and medical supervision to detect any unforeseeable risk or safety signals at the earliest possibility.

## 3 STUDY OBJECTIVES AND ENDPOINTS

### 3.1 Primary Objective

The primary objective of this study is:

- To evaluate the rate and the amount of nicotine absorbed (as assessed by maximum plasma concentration [ $C_{max}$ ] and area under the concentration-time curve [AUC] from start of product use to time of last quantifiable concentration [ $AUC_{(0-last)}$ ]) from THS 2.2 relative to CC, following single use of THS 2.2 and CC.

### 3.2 Secondary Objectives

The secondary objectives of this study are:

- To determine if  $C_{max}$  and  $AUC_{(0-last)}$  of the THS 2.2 are higher relative to NNS following single use of the THS 2.2 and NNS.
- To evaluate the difference on nicotine pharmacokinetic (PK) absorption parameters (AUC from start of product use extrapolated to time of last quantifiable concentration to infinity [ $AUC_{(0-\infty)}$ ] and partial AUC, where  $t'$  is the subject-specific time of maximum nicotine concentration following single use of the CC or NNS product [ $AUC_{(0-t')}$ ]) between the THS 2.2 and CC, as well as the THS 2.2 and NNS.
- To evaluate the time to the maximum concentration ( $t_{max}$ ) of nicotine for the THS 2.2 as compared to CC and to determine if the  $t_{max}$  for THS 2.2 is shorter as compared to NNS.
- To describe the terminal half-life ( $t_{1/2}$ ) of nicotine for the THS 2.2, CC, and NNS.
- To describe the differences on urge-to-smoke over time between the THS 2.2 and CC, as well as between the THS 2.2 and NNS.
- To describe product evaluation in the THS 2.2 and CC users.
- To describe the levels of carbon monoxide (CO) exposure for the THS 2.2, as compared to CC and NNS users.
- To monitor the safety during the study.

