#### 12.1.5 Significance Level for Inferential Analysis

For all endpoints, unless otherwise stated, statistical tests will be two-sided and conducted at the 5% significance level and all quoted confidence intervals (CIs) will be two-sided 95% CIs.

No formal adjustment of the test-wise alpha level for multiple testing is necessary, as no claim will be made based on the outcome of the individual tests.

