### 12.5.3 Descriptive Analysis

Primary endpoints will be summarized as described in [Section 12.1.3](#).

An analysis of variance (ANOVA) will be conducted on  $AUC_{(0-\text{last})}$  and  $C_{\max}$  endpoints in the natural logarithmic scale. The model will include terms for sequence, subjects within sequence, period and product exposure as fixed effect factors. The results of this analysis for each of  $AUC_{(0-\text{last})}$  and  $C_{\max}$  are presented in terms of adjusted geometric least square means and 95% CIs for the THS 2.2:CC and THS 2.2:NNS ratios.

This approach is consistent with the guidelines in the European Medicines Agency's guidelines for bioequivalence investigations ([EMA, 2008](#)) and FDA's Center for Drug Evaluation and Research ([FDA, 2001](#)). Carry-over effect will not be tested, as it cannot be statistically distinguished from the interaction between treatment and period in a 2x2 crossover design ([ICH E9, 1998](#)).

A sensitivity analysis will be conducted should there be 20% or more missing PK parameter values, by repeating the above analyses using mixed effects ANOVA model in the natural log scale, with a restricted maximum likelihood method to estimate mean differences and variances as suggested by FDA ([FDA, 2001](#)). Subjects within sequence will be used as random effects and fixed effects are period, sequence, and product exposure. To evaluate the sensitivity to the distributional assumptions, point and interval estimates will also be

Confidentiality Statement: Data and information contained in this document are considered to constitute trade secrets and confidential commercial information, and the legal protections provided to such trade secrets and confidential information are hereby claimed under the applicable provisions of applicable law. No part of this document may be publicly disclosed without the written consent of Philip Morris Products SA.

estimated by means of the percentile bootstrap technique, using 2000 bootstrap samples which preserve the number of subjects per sequence.

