### 12.6 Secondary Endpoints

#### 12.6.1 Secondary Endpoint Analysis Variables

Nicotine PK parameters will be derived as follows:

$t_{max}$  Time of maximum observed plasma concentration.  $t_{max}$  will be reported as long as there is at least one quantifiable concentration post-exposure

$AUC_{(0-t)}$  Area under the plasma concentration-time curve from zero to the subject-specific time to maximum nicotine concentration following single use of CC or NNS(linear trapezoidal method)

$AUC_{(0-\infty)}$  Area under the plasma concentration-time curve from start of product use extrapolated to infinite time, according to:

$$AUC_{0-\infty} = AUC_{0-last} + \left( \frac{C_{last}}{\lambda_z} \right)$$

Where  $C_{last}$  is the last quantifiable concentration and  $\lambda_z$  is the terminal elimination rate constant

$\lambda_z$  Terminal elimination rate constant, estimated by linear regression analysis of the natural log-transformed concentration-time data

$t_{1/2}$  Terminal elimination half-life, derived as  $\ln(2)/\lambda_z$

More details on PK parameter derivations will be provided in the SAP.

Subjective effects of using THS 2.2 as compared to the CC and to the NNS will be evaluated by analysing domain scores of QSU-brief and MCEQ. Full details of questionnaire domain scores derivation will be provided in the SAP.

Confidentiality Statement: Data and information contained in this document are considered to constitute trade secrets and confidential commercial information, and the legal protections provided to such trade secrets and confidential information are hereby claimed under the applicable provisions of applicable law. No part of this document may be publicly disclosed without the written consent of Philip Morris Products SA.

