## 12.6.3 Descriptive Analysis

In general, secondary endpoints will be summarized using the approach described in [Section 12.1.3](#).

The following analyses will be conducted in both Group-1 and Group-2 PK analysis sets:

- AUC(0-∞), AUC(0-t), and t1/2 will be analysed using the same approach adopted for the primary endpoints. No statistical analysis will be performed on the elimination rate constant λz. Data will be summarized and presented together with 95% CI.
- Hodges-Lehmann 95% CI estimates for the median tmax differences will be presented ([Lingling, 2008](#)).
- The use of random effects model is suggested in the context of the analysis of subjective effects of smoking ([Shiffman et al, 2004](#)). Mixed effects ANOVA with the same model terms as planned for the sensitivity analysis of the primary endpoints will be adopted for the analysis of QSU-brief, including all of the different assessment time points as repeated measurements. The analysis will not be adjusted for the assessment prior to T0 ([Fleiss et al, 1985](#)).
- Levels of exhaled CO and of blood COHb will be summarized by means of descriptive statistics reported by exposure. Analysis of COHb levels will be conducted using a mixed model for repeated measures, the same approach as for the QSU-brief.

The following analyses will be conducted only in Group-1 PK analysis set:

- Mixed effects ANOVA with the same model terms as planned for the sensitivity analysis of the primary endpoints will be adopted for the analysis of the MCEQ domain scores.

The following analyses will be conducted in only Group-2 PK analysis set:

- To test if the time to the maximum nicotine concentration in THS 2.2 is shorter than in NNS the following hypothesis will be evaluated:  
$$H_0: X_{THS} - X_{NNS} = 0 \quad H_A: X_{THS} - X_{NNS} < 0$$

Confidentiality Statement: Data and information contained in this document are considered to constitute trade secrets and confidential commercial information, and the legal protections provided to such trade secrets and confidential information are hereby claimed under the applicable provisions of applicable law. No part of this document may be publicly disclosed without the written consent of Philip Morris Products SA.

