#### Sample Size:

A total of 62 subjects will be randomized. This is calculated by adding up sample sizes separately estimated for each analysis.

A total of 44 subjects are needed to estimate the mean  $C_{\max}$  parameter ratio between THS 2.2 and CC with a 90% probability of obtaining a margin of error (95% CI) of at most  $\pm 20\%$ , assuming that THS 2.2 have a nicotine PK profile similar to CC ( $C_{\max}$  ratio equal to 1.00) and a 10% dropout rate.

A total of 18 subjects are needed to estimate the mean  $C_{\max}$  parameter ratio between THS 2.2

and NNS with a precision allowing for the lower bound of the 95% CI exceeding 1.00, with 90% power and assuming a 10% dropout rate. The anticipated geometrical  $C_{max}$  ratio between THS 2.2 and NNS is 1.55.

The sample size of this study is based on our current understanding of THS 2.1, the previous prototype of THS 2.2, where the within-subject coefficient of variation for nicotine  $C_{max}$  and  $AUC_{(0\text{-last})}$  was found to be approximately equal to 36% and 21%, respectively.

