#### **7.5.1.2 Biomarkers of Exposure to Nicotine**

Blood samples to measure nicotine in plasma will be taken as follows:

Single Use on Day 1 and Day 3:

A total of 16 blood samples will be taken for a 24-hour profile (Day 1 and Day 3). The first blood sample will be taken within 15 minutes prior to the single use ( $T_0$ ). Times of sampling are thereafter in relation to  $T_0$ :  $T_1$  after 2 minutes,  $T_2$  after 4 minutes,  $T_3$  after 6 minutes,  $T_4$  after 8 minutes,  $T_5$  after 10 minutes,  $T_6$  after 15 minutes,  $T_7$  after 30 minutes,  $T_8$  after 45 minutes,  $T_9$  after 60 minutes,  $T_{10}$  after 2 hours,  $T_{11}$  after 4 hours,  $T_{12}$  after 6 hours,  $T_{13}$  after 9 hours,  $T_{14}$  after 12 hours and  $T_{15}$  after 24 hours (this sample will be drawn during the day following product use, i.e., wash-out).

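### Cutting partial AUC at each subject's own reference tmax shifts the AUC(0-t') ratios below 1 even for identical products; the size depends on timing variability that the protocol does not give

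*Protocol*

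**What the plan says.** Section 3.2 lists partial AUC beside AUC(0-∞) in one secondary objective and fixes the cut-off: t' "is the subject-specific time of maximum nicotine concentration following single use of the CC or NNS product". The abbreviation list agrees. Section 12.6.1 gives the derivation as "Area under the plasma concentration-time curve from zero to the subject-specific time to maximum nicotine concentration following single use of CC or NNS", by linear trapezoid. The definition is the same wherever it appears.

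Section 12.6.3 says that AUC(0-∞), AUC(0-t') and t1/2 "will be analysed using the same approach adopted for the primary endpoints". Section 12.5.3 describes that approach as an ANOVA on the natural log scale: "The model will include terms for sequence, subjects within sequence, period and product exposure as fixed effect factors". Results are reported as THS 2.2:CC and THS 2.2:NNS ratios, and under section 12.1.5 "all quoted confidence intervals (CIs) will be two-sided 95% CIs".

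Section 7.5.1.2 sets the early sampling grid at 2, 4, 6, 8, 10, 15, 30, 45 and 60 minutes. Section 12.6.1 leaves further derivation detail to the SAP, but the choice of t' is already made in the protocol. No common cut-off is offered there, even as a sensitivity analysis.

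**The concern.** t' is read from the reference curve and then imposed on the THS 2.2 curve. If the reference was absorbed quickly on its day, t' is early and the THS 2.2 curve is cut while still low, which gives a large negative log ratio. If the reference was slow, t' is late. THS 2.2 is then ahead, but that lead is diluted by the area both curves have already accumulated. The two cases do not cancel on the log scale. Balancing the sequences does not help, because the reference product always supplies t', whichever period it falls in.

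At stake is how the only planned AUC of early uptake is read. The sample-size section assumes a profile similar to CC. If that is true, this ratio will tend to suggest slower early uptake from THS 2.2 than occurred. If the products truly differ, the artefact is mixed with the real difference and cannot be separated from it.

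**Working it through.** **1. The plan's own figures.** The protocol gives no figure for this bias, so the sample size is reproduced to fix the analysed numbers. For THS 2.2:CC the plan is "with a 90% probability of obtaining a margin of error (95% CI) of at most" ±20%, and the within-subject CV of Cmax and AUC(0-last) "was found to be approximately equal to 36% and 21%, respectively".

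- SD of a paired log difference = √(2·ln(1 + 0.36²)) = 0.494.
- The smallest n with P(t·s/√n ≤ ln 1.2) ≥ 0.90 is 40 (actual probability 0.92). Then 40 × 1.1 = 44, as stated.
- THS 2.2:NNS, ratio 1.55 and 90% power: n = 16, and 16/0.9 = 17.8, so 18, as stated.

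The analysed numbers are therefore about 40 and 16.

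**2. Why the sign is negative.** Take two curves from the same product in one subject: A peaks at time a, B at a later time b.

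- A is the reference: L₁ = ln[AUC_B(0–a)/AUC_A(0–a)].
- B is the reference: L₂ = ln[AUC_A(0–b)/AUC_B(0–b)].
- For identical products both labellings are equally likely. The mean log ratio is (L₁ + L₂)/2 = ½(G_A − G_B), where G_X = ln[AUC_X(0–b)/AUC_X(0–a)].

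Between a and b, curve B is still rising to its maximum and normally grows relatively more than A. So G_B > G_A and the mean is negative.

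**3. A hand example (illustrative shapes).** Both curves rise linearly to height 1 and stay there. A peaks at 6 min, B at 10 min.

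- t' = 6: AUC_A = 6/2 = 3; AUC_B = 6²/(2·10) = 1.8; test/reference = 1.8/3 = 0.60.
- t' = 10: AUC_A = 3 + 4 = 7; AUC_B = 10/2 = 5; test/reference = 7/5 = 1.40.
- Geometric mean = √(0.60 × 1.40) = √0.84 = 0.917, although the two labellings are symmetric.

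**4. Size by simulation.** Each scenario used 200,000 pairs of identical products on the protocol's grid, with linear trapezoid and t' at the observed reference maximum. Inputs from the protocol: half-life about 2 h (section 4.2), use lasting about 6 min (section 2.1.2), AUC CV about 21% (section 12.2). Assumed: the within-subject log-SD of timing, bi-exponential disposition with a fast phase, and measurement noise (10% unless stated).

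| Scenario (timing log-SD) | Ratio, subject's own t' | Ratio, common t' | CI wholly below 1, n=40 | n=16 |
|---|---|---|---|---|
| 6-min input (0.3) | 0.951 | 0.999 | 10.2% | 5.4% |
| 6-min input (0.5) | 0.899 | 1.001 | 19.8% | 8.2% |
| With 1-min lag (0.3) | 0.931 | 0.999 | 11.4% | 5.4% |
| Noise 25% (0.4) | 0.922 | 1.002 | 15.3% | 6.8% |
| No fast disposition phase (0.3) | 0.958 | 1.000 | 9.8% | 5.3% |
| 12 random puffs (0.3) | 0.932 | 0.999 | 9.5% | 4.6% |
| Duration and dose correlated 0.8 (0.3) | 0.951 | 1.000 | 29.1% | 12.8% |
| Duration and dose correlated 0.8 (0.5) | 0.898 | 1.000 | 51.2% | 18.4% |

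The nominal value in the last two columns is 2.5%. The CI lay wholly above 1 in fewer than 1% of the n=40 trials.

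First-order absorption gave milder shifts: about 0.99 at log-SD 0.2, 0.97 at 0.4, and 0.93 at 0.6 for an NNS-like profile. Across timing log-SD 0.2 to 0.6 the range is about 0.99 to 0.87. With no timing variation and no noise the ratio is 1.00.

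**5. Control.** Cutting at the THS 2.2 tmax instead gave the mirror image (about 1.003 to 1.26). A common t' at the group median reference tmax gave 0.996 to 1.003 in every scenario. The shift comes from which curve supplies t'.

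**The case against.** The best counter-argument is about weight. The effect depends on the day-to-day variability of reference tmax, which the protocol does not report, and at the low end it is about 1%. The shift is also usually smaller than the CI half-width. At timing log-SD 0.3 the SD of the log ratio was 0.42, so the half-width is 2.02 × 0.42/√40 = 0.134 with 40 subjects, against a shift of ln 0.951 = −0.050. With 16 subjects it is 2.13 × 0.42/4 = 0.224. Both points stand.

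It is also true that no decision rests on this parameter. Section 12.6.3 is descriptive, section 12.6.4 has no confirmatory analysis, and section 12.1.5 says no claim depends on individual tests. The hypotheses tested against NNS concern tmax, Cmax and AUC(0-last). Against NNS a downward shift works against what the sponsor expects (Cmax ratio 1.55).

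A reader might therefore infer too much: that early absorption cannot be evaluated at all, or that a planned test has an inflated error rate. The documents support neither. Rate is also covered by Cmax and tmax, which do not use t', and no test or success criterion is attached to AUC(0-t').

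Finally, a subject-specific t' does define a quantity of its own, exposure up to that subject's reference peak, and the SAP might add a sensitivity analysis. Neither removes the problem. The quantity is reported as a product ratio, and under the stated rule that ratio is not centred on 1 when the products are the same.

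**Conclusion.** The point holds for one descriptive secondary parameter. As defined, the AUC(0-t') ratios for THS 2.2:CC and THS 2.2:NNS are shifted below 1 for identical products whenever the absorption time course varies between days. The direction held in every curve model tried. It is not a theorem: an unusual pair of shapes, such as an early long plateau against a late sharp rise, could offset it.

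The size is conditional on assumptions. For a timing log-SD of 0.2 to 0.6 the shift is about 1% to 13%. The CI lies wholly below 1 in about 3.5% to 25% of trials with 40 subjects and about 3% to 10% with 16. Those rates are higher if duration of use and dose are strongly correlated. The practical effect in Group-2 is small. A ratio modestly below 1 should not be read as slower early uptake. The conclusions on Cmax, AUC(0-last), AUC(0-∞) and tmax are untouched.

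**What to change.** In sections 3.2 and 12.6.1, and in the synopsis and abbreviation list, define t' as one common time per comparison: the median CC tmax in Group-1 and the median NNS tmax in Group-2. Apply it to both products in every subject, with linear interpolation if the median falls between sampling times. Keep the subject-specific version as a supportive analysis, with a note that it is biased downwards. Make the change before the study statisticians are unblinded under section 6.4.

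The cost is one endpoint definition and a small change in PK programming, with no new samples or subjects. The downside is that t' no longer follows each subject's reference peak: late-peaking subjects are cut before their peak, and early-peaking subjects contribute some of their decline.

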### 3.3 Primary Endpoints

- Primary nicotine PK parameters (THS 2.2 vs. CC):
  - $C_{max}$ .

Confidentiality Statement: Data and information contained in this document are considered to constitute trade secrets and confidential commercial information, and the legal protections provided to such trade secrets and confidential information are hereby claimed under the applicable provisions of applicable law. No part of this document may be publicly disclosed without the written consent of Philip Morris Products S.A.

- AUC(0-last).

Evaluation criterion:

The study will be considered successful, if the 95% Confidence Intervals (CI) of the THS 2.2:CC ratio for the primary nicotine PK parameters are estimated with a precision of  $\pm 20\%$ .

### 3.4 Secondary Endpoints

- Primary nicotine PK parameters (THS 2.2 vs. NNS)
- Secondary nicotine PK parameters
  - AUC(0-∞).
  - Partial AUC(0-t').
  - tmax.
  - t1/2
- Subjective smoking effects:
  - Urge-to-smoke questionnaire (Questionnaire of Smoking Urges brief [QSU-brief]).
  - Product evaluation questionnaire (Modified Cigarette Evaluation Questionnaire [MCEQ]).
- CO exposure biomarkers: levels of exhaled CO and carboxyhemoglobin (COHb) in blood.
- Safety variables:
  - Incidence of adverse events (AEs)/serious adverse events (SAEs) and device event including THS 2.2 malfunction/misuse.
  - Respiratory symptoms: cough assessment by visual analogue and Likert scales and one open question.
  - Vital signs.
  - Spirometry.
  - Electrocardiogram (ECG).
  - Clinical chemistry, haematology, and urine analysis safety panel.
  - Physical examination.
  - Concomitant medication

Additional study assessments:

- Serology for human immunodeficiency virus 1/2 and Hepatitis B and C.

Confidentiality Statement: Data and information contained in this document are considered to constitute trade secrets and confidential commercial information, and the legal protections provided to such trade secrets and confidential information are hereby claimed under the applicable provisions of applicable law. No part of this document may be publicly disclosed without the written consent of Philip Morris Products S.A

- Urine pregnancy test (females only), urine cotinine test, urine drug screen.
- Alcohol breath test.
- Chest X-ray.
- Nicotine dependence to be assessed with the Fagerström Test for Nicotine Dependence (revised version).
- Cytochrome P450 2A6 activity (nicotine metabolic molar ratio) in plasma.

